9.3.3 Additional Data Collection

Other data points and associated times will be collected in addition to the analysis of the continuous data from the Starling SV system. Types of data points for collection are:

- Medical history
- Medications
- Volume of treatment fluid administered
- Urine output (to be recorded every 12 hours)
- Respiratory status
- Serum Creatinine level (every 24 hours +/- 4 hours , for 72 hour monitoring period and at 30 day discharge)
- Lactate level (per chart review, if available)
- Significant clinical events not previously identified for study data collection, e.g. cardiac arrest, CPR, intubation, extubation, placement of catheters (intravenous, arterial, urinary, etc), etc.
- Changes in mechanical ventilator status parameters

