## 5 SAMPLE SIZE

Subjects will be randomly assigned in a 2:1 ratio to treatment with Starling SV or to treatment with standard of care, stratified by time window of enrollment (0-6 hours, 6-12 hours, and 12-24 hours). The primary effectiveness endpoint for this study is fluid balance at ICU discharge.

Minimum enrollment ( $N_{\min}$ ) in the study will be set at 120 subjects (80 Starling SV and 40 control) to power at 80% for demonstration of superiority of means for the secondary endpoint of creatinine levels as a measurement of change from baseline at 72 hours. The secondary endpoint for change in creatinine levels at 120 evaluable subjects displays 80% power at a two-sided alpha level of 0.05 to demonstrate superiority of Starling SV under an assumption of an average treatment effect of -1.4 mg/dL with a standard deviation of 2.5 mg/dL.

Under an assumption of an average treatment effect of -2 L with a standard deviation of 3 L, the sample size of 120 evaluable subjects provides 92.7% power in a test of superiority of means for the primary effectiveness endpoint at a two-sided 0.05 level of significance.

The trial will incorporate a sample size re-estimation (SSR) at the time of the interim look (after 90 patients have been evaluated for the key secondary endpoint) based on promise for superiority in the key secondary endpoint. Sample size re-estimation, described in further detail in Section 3.1, will result in a maximum of 210 total evaluable subjects, or no more than 1.75 times the minimum of 120.

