## 7.3 METHODS FOR WITHDRAWALS, MISSING DATA, AND OUTLIERS

All reasonable efforts will be made to obtain complete data for all subjects; however, missing observations will occur due to death, loss to follow-up, withdrawal, non-adherence to the protocol, and possible non-evaluable assessments. Since this is unlikely due to the short follow-up time schedule and the consistent nature of data collection, missing data will not be imputed. However, should more than 5% of subjects be missing evaluable data for the primary endpoint, then as a sensitivity analysis to assess the impact of missing data on the primary endpoint treatment comparisons, treatment group comparisons on the primary endpoint will be performed where missing data are first imputed via multiple imputation linear regression using the FCS method in SAS. The multiple imputation model will use, as covariates in the imputation model, the demographic variables shown in the demographics table shell in Appendix A. A total of 10 complete datasets will be created for the multiple imputation and the primary endpoint treatment comparisons will be carried out within each imputed dataset; results will then be combined across imputed datasets using standard multiple imputation techniques in PROC MIANALYZE to obtain one treatment comparison p-value on the primary endpoint. Tables detailing missing data and analysis populations will be provided in the final report. Should the sensitivity analysis be required, it will also be provided in the final report.

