## 9.1 PRIMARY EFFICACY VARIABLE

The primary endpoint analysis is an evaluation of the difference between the two treatment groups in mean fluid balance (L) at 72 hours or ICU discharge, whichever occurs first. The following hypothesis will be tested:

$$\begin{aligned}H_0: \mu_c - \mu_t &= 0 \\H_a: \mu_c - \mu_t &\neq 0\end{aligned}$$

where  $\mu_t$  and  $\mu_c$  is the average fluid balance in the Starling SV and control groups, respectively. Statistical summaries will include means, medians, quartiles and standard deviation for each

treatment group, as well as 95% confidence interval of the difference between treatment group means. Subjects that enter the study on dialysis, or are on chronic dialysis, are excluded from this endpoint. A two-sample t-test will be used to test the null hypothesis at a two-sided 0.05 level of significance. A significant p-value combined with a lower sample mean for Starling SV than for the control group will indicate statistical superiority of Starling SV over the control with respect to the primary endpoint. Fluid balance will be analyzed under sensitivity analyses not intended for formal hypotheses testing.

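### SAP 7.3 does not put treatment arm in the imputation model, so the missing-data sensitivity analysis would shrink the fluid-balance difference toward zero

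*SAP*

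**What the plan says.** SAP 7.3 does not impute missing values in the main analysis. If more than 5% of subjects lack evaluable primary-endpoint data, it adds a sensitivity analysis: regression-based multiple imputation (FCS), 10 completed datasets, the arm comparison run in each, and the results combined into one p-value. On the model it says: "The multiple imputation model will use, as covariates in the imputation model, the demographic variables shown in the demographics table shell in Appendix A".

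SAP 8.1 sets out the demographic variables: age, body size, SOFA and qSOFA, FiO2, Glasgow Coma Score, sex, race, infection and SIRS items, and similar baseline characteristics. Treatment group is what they are tabulated by; it is not one of them. The enrollment-window stratum and baseline creatinine are not listed there either. Neither section mentions imputing each arm separately.

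The endpoint is "mean fluid balance (L) at 72 hours or ICU discharge, whichever occurs first" (SAP 9.1), and the test is specified thus: "A two-sample t-test will be used to test the null hypothesis at a two-sided 0.05 level of significance". On why values go missing, SAP 7.3 says "missing observations will occur due to death, loss to follow-up, withdrawal, non-adherence to the protocol", among other causes.

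**The concern.** An imputation model should contain every variable in the analysis that follows it. Here that analysis compares arms. If arm is left out, a missing treated value and a missing control value with the same baseline profile are drawn from the same distribution. Randomized baseline covariates carry no information about arm, so on average the imputed values show no treatment difference. Mixing them with the observed values dilutes the difference.

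This is the only missing-data analysis that the SAP specifies in detail. If it returns a smaller effect and a larger p-value, a reader will conclude that the result depends on the missing subjects, when part or all of the change may come from the model.

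**Working it through.** **Inputs.** SAP 5: difference -2 L, SD 3 L, 80 Starling SV and 40 control, two-sided 0.05. SAP 7.3: 10 imputations, 5% trigger. The documents give no expected rate of missing data or early death, so 5% to 30% is an assumed range.

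**Reproducing the plan's figure.** SAP 5 says that "the sample size of 120 evaluable subjects provides 92.7% power in a test of superiority of means". The noncentrality is 2 / (3 × √(1/40 + 1/80)) = 2 / 0.581 = 3.44. The noncentral t with 118 degrees of freedom gives power of 92.71%, so the stated 92.7% is reproduced.

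**Expected difference when arm is left out.** Let d be the true difference, mT and mC the missing fractions in the treated and control arms, and w the treated share of the observed subjects. An imputed value has mean w·μT + (1-w)·μC in either arm. Then:

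- treated mean = (1-mT)·μT + mT·[w·μT + (1-w)·μC]
- control mean = (1-mC)·μC + mC·[w·μT + (1-w)·μC]
- difference = d × [1 - mT(1-w) - mC·w]

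With mT = mC = m this is d × (1-m).

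**Equal missingness.** The formula was checked by simulation: 2,000 trials per setting, 80/40, values missing at random within arm, Bayesian linear-regression imputation, 10 datasets, Rubin's rules. The table uses four baseline covariates that explain none of the variance. Percentages are the share of trials with p < 0.05.

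| Missing in each arm | Formula, no arm | Simulated, no arm | Simulated, with arm | Complete cases |
|---|---|---|---|---|
| 5% | -1.90 L | -1.91 L, 90.4% | -2.01 L, 91.8% | 91.9% |
| 10% | -1.80 L | -1.79 L, 84.3% | -1.99 L, 88.4% | 89.0% |
| 15% | -1.70 L | -1.69 L, 79.0% | -2.00 L, 88.0% | 88.4% |
| 20% | -1.60 L | -1.59 L, 69.9% | -1.99 L, 83.8% | 85.1% |
| 30% | -1.40 L | -1.40 L, 50.3% | -2.01 L, 78.2% | 81.8% |

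If the covariates explain 20% of the variance, the result at 20% missing is -1.60 L without arm and -2.00 L with it. Better baseline prediction does not cure the problem.

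**Unequal missingness.**

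- 20% treated, 5% control: w = 64/102 = 0.627; factor 1 - 0.20×0.373 - 0.05×0.627 = 0.894; difference -1.79 L.
- 5% treated, 20% control: w = 76/108 = 0.704; factor 1 - 0.05×0.296 - 0.20×0.704 = 0.844; difference -1.69 L.
- 0% treated, 20% control: w = 80/112 = 0.714; factor 1 - 0.20×0.714 = 0.857; difference -1.71 L.

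The last case matters because SAP 6.4 makes the per-protocol set primary and requires 72 hours of monitoring only in the treatment group. If imputation is run in that set, which SAP 7.3 does not specify, mainly control values would be imputed. Only 8 of 120 subjects (6.7%) are then missing, yet the estimate shrinks by 14%.

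**The case against.** **The omission is inferred.** SAP 7.3 points to a table shell that is not in the text available for review, and it never says that arm is excluded. This stands as a limit on certainty. But SAP 8.1 lists the demographic variables without arm, and a programmer following both sections literally would leave it out. An intention to include arm should be written down.

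**The consequence is limited.** The analysis runs only above 5% missing, and SAP 9.1 says that fluid-balance sensitivity analyses are not for formal testing. Near the trigger the loss is about 0.1 L. The pull is toward no effect, so it cannot by itself create a false claim for the device. Both documents expect little missing data, and the 20% and 30% rows have no support in them. All of this stands and sets the size of the point.

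**The covariates are more than demographics.** The list includes SOFA and other severity measures. That is true, but they do not identify the arm.

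**Stronger readings that a reader might infer.** One is that counting early deaths as missing pulls the difference toward zero. It does not: deaths enlarge the missing fraction, and any bias from their being informative could go either way. Another is that the main analysis certainly drops early deaths although their balance to death is on record. The documents show neither. No section says how balance is scored for a subject who dies first, and Protocol 9.3.3 lists treatment-fluid volume and 12-hourly urine output without saying that a total is closed out at death. A third is that measuring balance to death would settle the matter. It would not restore treated subjects whom the 72-hour monitoring condition in SAP 6.4 removes, and it is a debatable choice, since a very early death may score as a low balance.

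**Conclusion.** The concern holds for the imputation model. Followed as written, SAP 7.3 gives a sensitivity estimate biased toward zero: by about the missing fraction when the arms are equally affected, and by more than the overall missing fraction when losses fall mainly on controls. On the planned -2 L this is about 0.1 L at 5% missing, 0.2 L at 10% and 0.4 L at 20%, and about 0.29 L if only controls are affected at 20%. It becomes material from roughly 15% to 20% equal missingness.

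These sizes assume the SAP's effect and SD, 80/40 subjects, values missing at random within arm, and that the Appendix A shell adds no arm term. The primary p-value and the secondary testing sequence are unaffected. What is lost is the ability of this analysis to answer its own question.

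The handling of deaths before 72 hours is a separate gap and a secondary one. Protocol 12.6 and SAP 6.4, 7.3 and 9.1 do not together say whether such a subject is excluded, missing or scored. SAP 9.2.1.4 treats ICU deaths separately for length of stay, so death cannot simply be assumed to count as ICU discharge.

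**What to change.** In SAP 7.3, replace the covariate sentence with one that either imputes separately by randomized arm or includes arm as a covariate. With about 40 controls and a long covariate list, including arm may be the more stable option. Add the enrollment-window stratum, baseline creatinine, and the treatment-fluid and urine volumes recorded before data stop. State the analysis set in which imputation is run.

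In the simulations, adding arm alone brought the estimate back to about -2.0 L at every rate tried. The gain from the other variables was not tested; they are recommended because they should predict the missing value or belong to the design.

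Separately, reconcile Protocol 12.6 with SAP 6.4, 7.3 and 9.1 so that one rule says how a death before 72 hours enters the primary endpoint and each analysis set. Which rule to adopt is for the trial team to decide and justify.

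The imputation change costs a few lines of SAP text and a few more variables in the imputation call. The stratum, creatinine, fluid and urine data are already collected (Protocol 8.6, 9.1 and 9.3.3). Both changes should be settled before unblinding.

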## 7.4 PROTOCOL VIOLATIONS

A protocol violation is a failure to comply with the requirements specified within this clinical study protocol. Protocol violations will be summarized in the CSR. This summary will include the number and percent of subjects (overall and by site) with each violation type for the ITT analysis set. Protocol violations, according to section 14.2 of the protocol and the Protocol Deviation CRF, include:

- Failure to obtain subject's informed consent prior to any study-related activities;
- Subject did not meet the inclusion and/or exclusion criteria and were enrolled;
- Failure to conduct protocol required clinical test or assessment;
- Failure to complete protocol required assessments within the required time frame
- Failure to perform assessment or test according to the protocol
- Failure to report serious adverse events according to protocol requirements.

### 7.5 MULTIPLE COMPARISONS AND MULTIPLICITY

It is recognized that with a multiplicity of tests comes inflation in the chance of a false finding. Therefore, formal statistical testing will only be done for the following secondary endpoints:

- Changes in serum creatinine level from baseline to 72 hours (key secondary endpoint)
- Requirement for renal replacement therapy (RRT)
- Requirement for ventilator use
- Length of ICU stay (days) until subject is medically ready for discharge
- Number of hours with ventilator use (30-day period)
- Number of hours with vasopressor use

These endpoints will be tested in a hierarchical (sequential) manner in the order given above (and testing will only proceed if a significant beneficial treatment effect is detected in the primary endpoint). Specifically, the first secondary endpoint (change in creatinine) will be compared between treatments at a two-sided 0.05 level of significance. If significant in the direction favoring Starling SV, then Starling SV will be considered beneficial on change in serum creatinine level, and the next endpoint (ICU stay) will be compared between treatments at a two-sided 0.05 level of significance; otherwise the statistical testing will stop and Starling SV will not be considered statistically significantly beneficial on any secondary endpoint. If the treatment comparison is able to proceed to this next secondary endpoint of ICU stay, it will be carried out at the two-sided 0.05 level of significance. If the treatment comparison is significant in the direction favoring Starling SV, then Starling SV will be considered beneficial on this endpoint and testing will proceed in a similar manner for the remaining endpoints; otherwise, treatment comparisons will stop and Starling SV will not be considered beneficial on this second secondary endpoint of ICU stay nor on all endpoints after it in the above sequence.

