12.4 Secondary and Exploratory Endpoints

Secondary objectives that have been pre-specified to be included in the formal statistical analysis will be tested in sequential fashion using the Holms step-down procedure for type-I error rate correction if and only if the primary objective passes according to the criteria outlined above. At the conclusion of the trial, the key secondary endpoints will be ordered sequentially from most significant to least significant. The endpoints will then be tested in order at adjusted levels of significance (i.e. E1: 0.05/k, E2: 0.05/k-1; E3: 0.05/k-2, where k=number of specified endpoints). Once an endpoint fails, all following endpoints will not be tested. Following is a list of key secondary endpoints:

Following is a list of key secondary endpoints for formal testing:

- Length of ICU stay (days) until subject is medically ready for discharge
- Number of days free from ventilator use (30 day period)
- Requirement for mechanical ventilation
- Number of days free from vasopressor use
- Changes in serum creatinine levels from baseline
- Requirement for renal replacement therapy (RRT)

Additional secondary endpoint have also been identified for testing, but will not be included in the formal statistical testing procedures for key secondary endpoints:

- Incidence of Adverse Events (AE)

- Number of ICU readmissions
- Mortality rate
- Mean volume of treatment fluid
- Incidence of Major Adverse Cardiac Event (MACE)
- Discharge location
- Mean difference in fluid balance at ICU discharge

Additional sub-analyses have been planned for the primary and key secondary endpoints. Primary and secondary endpoints will also be evaluated by the following subgroup analysis:

- Patient disease state
- Patients determined to be fluid responsive vs non-fluid responsive
- AKI measures in patients determined to increase serum creatinine levels from baseline vs decrease serum creatinine levels from baseline
- Enrollment time frame

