## 2 SUMMARY

TITLE	Evaluation of fluid volume in patients with sepsis and refractory hypotension.
PREFACE	
This Statistical Analysis Plan (SAP) describes the planned analysis and reporting for Cheetah Medical, Inc. protocol PRO-0001 (Fluid Responsiveness Evaluation in Sepsis-associated Hypotension [FRESH] Fluid Trial). This study is being completed to assess the safety and efficacy in using Starling SV for dynamic assessment of fluid responsiveness in the treatment of septic patients with refractory hypotension.
 
The following documents were reviewed in preparation of this SAP:
 
 
• Clinical Research Protocol PRO-0001, issued 30OCT2017
 
• Case report forms (CRFs) issued 01DEC2017 for Protocol PRO-0001
 

PURPOSE	The purpose of this SAP is to outline the planned analyses in support of the Clinical Study Report (CSR) for protocol PRO-0001. Exploratory analyses not necessarily identified in this SAP may be performed to support the clinical development program. Any post-hoc, or unplanned, analyses not identified in this SAP will be clearly identified in the respective CSR or manuscript.
STUDY OBJECTIVES	The objective of this study is to assess the mean difference in fluid balance at 72 hours or ICU discharge, whichever occurs first, and associated patient outcomes, based on a dynamic assessment of fluid responsiveness in septic patients with refractory hypotension in an ICU setting.
STUDY ENDPOINTS	
Primary: Fluid balance (L) at 72 hours or ICU discharge, whichever occurs first
 
Secondary:
 
 
1. Changes in serum creatinine level from baseline to 72 hours (key secondary endpoint)
 
2. Requirement for renal replacement therapy (RRT)
 
3. Requirement for ventilator use
 
4. Length of ICU stay (days) until subject is medically ready for discharge
 
5. Number of hours with ventilator use (30-day period)
 
6. Number of hours with vasopressor use
 
 
Not for Formal Testing:
 
 
1. Incidence of Adverse Events (AE)
 
2. Number of ICU readmissions
 
3. 30 day in-hospital Mortality rate
 
4. Volume of Treatment Fluid
 
5. Incidence of MACE
 
6. Discharge location
 
7. Mean difference in fluid balance at ICU discharge
 

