### 6.5 SAFETY

Subject will be included in the safety group if they are in the ITT analysis population and study treatment was at least attempted. This is the primary analysis population for safety, including adverse events (this is a change from the protocol, where it states that adverse events will be reported on all enrolled patients; it has been since felt that this could underreport the true adverse event rates in patients to whom randomized treatment was attempted). Patients are analyzed under the treatment received.

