## 9.2 SECONDARY EFFICACY VARIABLES

### 9.2.1 FOR FORMAL TESTING USING THE SEQUENTIAL APPROACH

If a significant beneficial Starling SV effect is found in the primary endpoint, the following secondary endpoints will be compared between treatments in the sequential manner discussed above.

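### SAP 7.5 names two different second steps for its fixed-sequence test (RRT in the list, ICU stay in the decision rule) and does not say that it replaces the protocol's Holm procedure

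*SAP*

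**What the plan says.** SAP 7.5 lists the formally tested secondary endpoints as creatinine change, RRT, ventilator requirement, length of ICU stay, ventilator hours and vasopressor hours. It then states: "These endpoints will be tested in a hierarchical (sequential) manner in the order given above". Testing starts only if the primary endpoint shows a significant benefit, and a secondary claim needs significance in the direction favouring Starling SV.

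The decision rule that follows tests creatinine at two-sided 0.05 and, if it succeeds, continues: "and the next endpoint (ICU stay) will be compared between treatments at a two-sided 0.05 level of significance". It names ICU stay as the next step once more. It closes by saying that, if that test fails, Starling SV "will not be considered beneficial on this second secondary endpoint of ICU stay nor on all endpoints after it in the above sequence".

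SAP 2, SAP 4.2.2.1 and the order of subsections 9.2.1.1 to 9.2.1.6 all follow the list. None of them states a testing rule. SAP 9.2.1 says only that "the following secondary endpoints will be compared between treatments in the sequential manner discussed above", which leads back to 7.5.

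Protocol 12.4 sets a different procedure. The secondary endpoints "will be tested in sequential fashion using the Holms step-down procedure for type-I error rate correction", again only if the primary succeeds, and "the key secondary endpoints will be ordered sequentially from most significant to least significant". The levels are 0.05/k, 0.05/(k-1) and so on, and six endpoints are listed.

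**The concern.** A fixed-sequence procedure can test every step at the full 0.05 because the order is set in advance. Here the order is stated twice, in two ways, within one section. The list puts RRT second. The decision rule puts ICU stay second, three times, so it does not read as a single slip. It also leaves the place of RRT and ventilator requirement unclear. Its stopping clause covers endpoints after ICU stay in the list, and these two come before it.

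The protocol adds a third candidate. Holm orders the endpoints by observed p-value and starts at 0.05/6, so under it even the creatinine claim could differ. SAP 7.5 does not mention Holm. Elsewhere the SAP does announce a departure: in 6.5 it says of the safety population that "this is a change from the protocol, where it states that adverse events will be reported on all enrolled patients". No section says which document governs, and SAP 3.2 refers to analyses identified in both.

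At stake is which secondary benefits may be claimed if the primary succeeds. Creatinine matters most, because it sets the minimum sample size and drives the sample size re-estimation.

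**Working it through.** **The plan's own power figures.** Inputs from SAP 5: 80 versus 40 subjects, two-sided 0.05; creatinine effect 1.4 mg/dL with SD 2.5; fluid balance effect 2 L with SD 3. The noncentrality of the two-sample t-test is effect / (SD × √(1/80 + 1/40)), and the square root is 0.1936.

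- Creatinine: 1.4 / (2.5 × 0.1936) = 2.89, power 81.8% (stated: 80%).
- Primary: 2 / (3 × 0.1936) = 3.44, power 92.7% (stated: 92.7%).

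Both reproduce, and neither is in dispute.

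**How often the two SAP orders disagree.** Order A is the list. Order B moves ICU stay to second and keeps the rest in list order. If creatinine is not significant, both stop and agree. If it is, the other five endpoints give 2⁵ = 32 patterns:

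- ICU-stay claim differs when ICU stay is significant but RRT and ventilator requirement are not both significant: 3 × 4 = 12 patterns.
- RRT claim differs when RRT is significant and ICU stay is not: 2 × 4 = 8 patterns.
- Ventilator-requirement claim differs when RRT and ventilator requirement are significant and ICU stay is not: 4 patterns, all within the previous 8.
- The last two endpoints never differ.

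The total is 12 + 8 = 20 of these 32 patterns, or 20 of all 64. If the rule is read literally, as ICU stay and then only the endpoints listed after it, it differs from the list in 16 + 8 = 24: all 16 patterns with RRT significant, and 8 with RRT not significant but ICU stay significant.

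**Examples.** The primary has passed, all effects favour Starling SV, and p-values not shown are 0.20. Holm levels for six endpoints are 0.0083, 0.0100, 0.0125, 0.0167, 0.0250 and 0.0500.

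| p-values | List order | ICU stay second | Holm |
|---|---|---|---|
| creatinine 0.03, ICU stay 0.03 | creatinine | creatinine, ICU stay | none |
| creatinine 0.03, RRT 0.03 | creatinine, RRT | creatinine | none |
| creatinine 0.20, RRT 0.005 | none | none | RRT |
| creatinine 0.03, RRT 0.005 | creatinine, RRT | creatinine | RRT |

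**Error if the order is chosen afterwards.** Suppose creatinine passes and neither RRT nor ICU stay has a true effect. A claim needs the favourable direction, so one pre-set second step gives a false claim with probability 0.025. Choosing between the two after seeing results gives 1 − (1 − 0.025)² = 4.94% if they are independent. Simulation gives 4.2% at correlation 0.7. The bound under any dependence is 0.025 + 0.025 = 5%.

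**Creatinine power under Holm.** Its level lies between 0.05/6 and 0.05, so its power lies between 58.4% and 81.8% (same t-test). Simulation with six independent endpoints gives about 60% if the other five have no effect, and about 72% if all share the creatinine effect size. The SAP's ANCOVA would shift these figures by an amount the documents do not give.

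**The case against.** The SAP leans strongly towards one order. The list appears in SAP 2, 4.2.2.1 and 7.5 and is matched by the subsections of 9.2.1. The governing sentence of 7.5 adopts it, and the stopping clause points back to it. ICU stay heads the list in protocol 12.4, so its place in the decision rule may be left over from another ordering. The rule also says the remaining endpoints follow in a similar manner, which could cover RRT and ventilator requirement. All this supports the list as the right correction. It does not change what the operative rule says.

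On Holm, the SAP sets out a complete alternative, and both documents power creatinine at 0.05. That fits a fixed sequence, and it means protocol 12.1 and 12.4 were already out of step. The 58% to 82% range applies only if Holm governed. This stands, but a change of error-control method still has to be stated.

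The figures have limits. The pattern count is not a probability. With creatinine power of 82%, independence, and a common chance q of a significant favourable result for each later endpoint, the two orders disagree in 0.82 × [q(1 − q²) + q(1 − q)] of trials: about 4% at q = 0.025, 51% at q = 0.5 and 34% at q = 0.82. The 4.9% is close to a worst case and presumes that someone picks the order after seeing results. SAP 2 also says the study is not meant to support a regulatory filing. These points bear on weight: they keep the matter from being severe, but they do not remove it.

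**Conclusion.** The concern holds and should be fixed. The decision rule in SAP 7.5 contradicts the list it is meant to apply, no other section resolves this, and the replacement of Holm is undeclared. If creatinine is significant, the same data can support different claims on ICU stay (12 patterns), RRT (8) and ventilator requirement (4). A data-driven choice at step two would roughly double the false-claim rate, from 2.5% to 4.9%. That figure assumes creatinine has passed, no true effect on RRT or ICU stay, and independence; 5% is the ceiling.

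Each procedure controls error if it alone is fixed in advance. The weakness is that the documents fix more than one. Within the SAP only the claims after creatinine are open; between the SAP and the protocol, the creatinine claim is open too. The primary analysis is untouched.

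**What to change.** In SAP 7.5, replace the ICU-stay wording so that the decision rule follows the list: creatinine, RRT, ventilator requirement, ICU stay, ventilator hours, vasopressor hours, each at two-sided 0.05 and stopping at the first failure. Add a sentence that fixed-sequence testing replaces the Holm procedure of protocol 12.4, marked as a change from the protocol in the way SAP 6.5 does, and amend protocol 12.4 to match.

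Do this before anyone sees secondary results by arm, and no later than database lock. Because SAP 3.1.1 tests the primary endpoint at 120 subjects even if enrolment is extended, it is safest to finish before that test.

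The cost is a few sentences in the SAP and a short protocol amendment, with no new data and no change to the sample size or the interim rule.

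Separately, and carrying no weight in this point, the creatinine time point should be made the same in SAP 3.1.1, 7.5 and 9.2.1.1 before the interim creatinine analysis. The first two use 72 hours; the last also allows ICU discharge if earlier.
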